10.9 Patient Reported Outcomes

The following instruments will be used to collect patient reported outcomes (PROs): SF-36 version 2 (SF-36v2) and FACIT-F. Missing data for each measurement will be handled as described in Section 6.3.

The following exploratory analyses of PROs will be performed:

- mean change from baseline to each applicable post-baseline time point in the SF-36v2 Mental Component Summary (MCS), Physical Component Summary (PCS) and eight individual domain measures;
- mean change from baseline to each applicable time point in the FACIT-F total score;

- percentage of subjects without a decrease from Baseline to Final Treatment Visit in the SF-36v2 PCS and MCS that is greater than or equal to the minimally important difference (MID) of five points.

The SF-36v2 measures dimensions of a patient's functional health and well-being in 8 domains and also provides 2 summary scores that characterize a patient's mental (MCS) and physical (PCS) health status. The score for each of the 8 domains ranges from 0 to 100 and will be normalized according to the user manual. The standardization of the normalized scores will provide the norm-based scores with a mean of 50 and a SD of 10. The two summary scores are based on the norm-based scores. Per the SF-36v2 instrument manual, score for any item with multiple responses will be set to "missing." Subject's responses to the SF-36v2 will be summarized for the PCS and MCS measures and the 8 individual domain measures.

The FACIT-F is a symptom specific instrument with a focus on measuring fatigue in a variety of chronic diseases or health conditions. Its 13-item-version assesses peripheral, central, or mixed fatigue and yields a summed total score ranging between 0 and 52. Higher FACIT-F scores indicate a lesser degree of fatigue. Notice that item 7 (I have energy) and item 8 (I am able to do my usual activities) are reversed scored.

Summary statistics (n, mean, SD, median, minimum and maximum) for the mean change from baseline to each applicable visit will be provided for the FACIT-F score and the SF-36v2 PCS and MCS scores.

An MID of -5 will be used for the change from Baseline to Final Treatment Visit in the SF-36v2 PCS and MCS. The percentage of subjects with a change from Baseline to Final Treatment Visit > -5 will be presented along with 95% confidence intervals.

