The FACIT–F is a symptom specific instrument with a focus on measuring fatigue in a variety of chronic diseases or health conditions. It was originally developed from interviews with oncology patients and clinical experts to assess anemia-associated fatigue. Its 13-item-version assesses peripheral, central, or mixed fatigue with a recall period of 7 days and yields a summed total score ranging between 0 and 52. Higher FACIT–F scores indicate a lesser degree of fatigue. Completion of the FACIT–F (version 4) should require approximately 5 – 10 minutes.

Assignment of Subject Numbers

A subject number is assigned at screening via IRT. Screening numbers will be unique 4-digit numbers and will begin with 1001, with the first 2 digits representing the investigative site and the last 2 digits representing the subjects at that site. Enrolled subjects will keep their screening number as their subject number.

Study Drug Dispensation

Study drugs will be dispensed at the visits as indicated in [Table 7](#).

Study Drug Returned for IRT Reconciliation

At each visit noted in [Table 7](#), the number of tablets of ABT-450/r/ABT-267, ABT-333, and RBV (if applicable) remaining in each kit (blister card for DAAs or bottle for RBV) will be entered into the IRT system. Additional information regarding treatment compliance can be found in Section [5.5.6](#).

Archive Samples

Archive plasma and serum samples will be collected at the study visits, indicated in **Table 7**. Archive plasma and serum samples are being collected for possible additional analyses, including but not limited to, study drug or metabolite measurements, viral load, safety/efficacy assessments, biomarkers of inflammation, HCV gene sequencing, HCV resistance testing, and other possible predictors of response, as determined by the Sponsor.

Specific instructions for preparation and storage of archive samples will be provided by the central laboratory, the Sponsor, or its designee.

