6.3 Missing Data Imputation

No data will be imputed for any efficacy or safety analyses except for the PRO questionnaires, for analyses of the HCV RNA endpoints, and for analysis of the persistence of resistance. If a respondent answers at least 50% of the items in a multi-item scale of the SF-36v2, the missing items will be imputed with the average score of the answered items in the same scale. In cases where the respondent did not answer at least 50% of the items, the score for that domain will be considered missing. Similarly, the missing items of the FACIT-F questionnaire will be imputed with the average score of the answered items in the same scale as long as more than 50% (≥ 7 out of 13) of the items in the scale are answered. The SF-36v2 Mental and Physical Component Summary measures will not be computed if any domain is missing.

HCV RNA values will be selected for an SVR analysis based on visit windows as defined in Section 6.2. When there is no HCV RNA value in a visit window based on defined visit windows, the closest values before and after the window, regardless of the value chosen for the subsequent and preceding window, will be used for the flanking imputation described below.

If a subject has a missing HCV RNA value at a post-Day 1 visit but with undetectable or unquantifiable HCV RNA levels at both the preceding value and succeeding value, the HCV RNA level will be considered undetectable or unquantifiable, respectively, at this visit for this subject. In addition, if a subject has an unquantifiable HCV RNA level at the preceding value and an undetectable HCV RNA level at the succeeding value, or vice versa, the HCV RNA level will be imputed as unquantifiable at this visit for this subject. For SVR analysis, if there is no value in the appropriate window after flanking imputation but there is an HCV RNA value after the window, then it will be imputed into the SVR window. Subsequent to this flanking imputation, if a subject is missing a value for the visit window associated with the analysis, the subject will be imputed as a visit failure (i.e., not undetectable or unquantifiable).

If a subject starts another treatment for HCV, then all HCV RNA values for this subject measured on or after the start date of the new HCV treatment will be excluded from analyses. The subject will be considered a failure for summaries of viral response at all time points after the start of the new HCV treatment.

HCV RNA < LLOQ Analyses for SVR

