10.4 Secondary Efficacy Analyses

The following analyses of secondary efficacy endpoints will be performed on the ITT-II population:

- The percentage of subjects achieving SVR₁₂ (HCV RNA < LLOQ 12 weeks after the last actual dose of study drug). The simple percentage of subjects

achieving SVR₁₂ will be calculated and a two-sided 95% confidence interval of the percentage will be computed based on Wilson's score method.

- The mean change from baseline in quality of life and fatigue to Post-Treatment Week 12 and to the Post-Treatment Week 24 (assessed by Short-Form 36 Version 2 health survey [SF-36v2] and the Functional Assessment of Chronic Illness Therapy – Fatigue [FACIT–F] questionnaires, respectively) will be assessed by subjects' baseline fibrosis stage, as described in Section 10.8.
- Adherence to ABT-450/r/ABT-267 and ABT-333 combined and adherence to RBV within the Treatment Period will be calculated as the percentage of tablets taken relative to the total tablets expected to be taken, as described in Section 9.2.

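### The FACIT-F item key in SAP 10.9 is ambiguous and, read literally, contradicts the stated direction of the score behind a secondary endpoint

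*SAP*

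**What the plan says.** SAP 10.9 introduces the instrument in three steps. On content: "Its 13-item-version assesses peripheral, central, or mixed fatigue". On range: it "yields a summed total score ranging between 0 and 52". On direction: "Higher FACIT-F scores indicate a lesser degree of fatigue". Protocol 5.3.1.1 gives the same range and direction (higher FACIT-F "scores indicate a lesser degree of fatigue") and names version 4, but states no item key.

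The next sentence of SAP 10.9 is the only FACIT-F item rule in either document: "item 7 (I have energy) and item 8 (I am able to do my usual activities) are reversed scored". Neither document gives the response options, how they are coded, or the text of the other 11 items. For SF-36v2, the same section sends the programmer to the user manual for scoring. It gives no such pointer for FACIT-F.

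SAP 6.3 fills missing FACIT-F items with the mean of the answered ones, "as long as more than 50% (≥ 7 out of 13) of the items in the scale are answered".

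SAP 10.4 lists as a secondary analysis "The mean change from baseline in quality of life and fatigue to Post-Treatment Week 12 and to the Post-Treatment Week 24", by baseline fibrosis stage. Protocol 8.1.2.2 supplies the model: an ANCOVA with fibrosis stage as factor, and baseline score and SVR12 status as covariates. SAP 10.4 refers to Section 10.8 for the description, but 10.8 covers resistance. The patient-reported outcome text is in 10.9, which labels its analyses exploratory.

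**The concern.** Both named items are positively worded: one is about having energy, the other about managing usual activities. A respondent who agrees with them is less fatigued, which is the direction the total is meant to have. In ordinary usage, reverse scoring an item means computing 4 minus the response. Applied to these two items under agreement coding, that makes them count toward more fatigue and conflicts with the sentence just before.

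The endpoint is a mean change, so its sign and size are the result. A wrong key could report improvement after treatment as worsening, or shrink it, and could do the same to the differences between fibrosis stages.

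**Working it through.** **Inputs.** From SAP 10.9: 13 items, total 0 to 52, higher means less fatigue, items 7 and 8 reversed. Assumed, because the documents do not say: the other 11 items are fatigue-worded and, except where noted, responses are coded 0 to 4 upward with agreement.

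**The plan's own range.** 52 / 13 = 4, so each item runs 0 to 4, and 13 × 4 = 52. This reproduces the stated range. Reversing an item leaves its 0 to 4 range unchanged, so the range alone cannot show which key is right.

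**Notation.** N is the sum of the 11 fatigue-worded responses (0 to 44). P is the sum of items 7 and 8 (0 to 8). Both are on the agreement scale. No fatigue is N = 0, P = 8. Maximum fatigue is N = 44, P = 0. A one-point improvement on every item lowers N by 11 and raises P by 2.

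| Reading of the rule | Total | No fatigue | Maximum fatigue | One-point improvement per item |
|---|---|---|---|---|
| Intended direction | (44 − N) + P | 52 | 0 | +11 + 2 = +13 |
| A. Upward coding, only 7 and 8 reversed | N + (8 − P) | 0 | 52 | −11 − 2 = −13 |
| B. Upward coding, all 13 reversed | (44 − N) + (8 − P) | 44 | 8 | +11 − 2 = +9 |
| C. Responses stored descending, only 7 and 8 reversed | (44 − N) + P | 52 | 0 | +13 |
| D. Reversed means keyed opposite to the other 11 | (44 − N) + P | 52 | 0 | +13 |

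**Reading A.** N + 8 − P = 52 − [(44 − N) + P], so the total is exactly 52 minus the intended score and every change has the opposite sign.

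**Reading B.** The direction is right, but the change is short by 4 of 13 points: 4 / 13 = 31%. Consistent responders fall between 8 and 44, inside the stated range, so nothing looks out of bounds.

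**Effect on the ANCOVA.** This was illustrated on simulated data for 600 subjects with invented values, so only the pattern matters. Under A, the mean change went from +3.13 to −3.13 and the F4 versus F0-F1 contrast from −2.31 to +2.31. F (4.116) and p (0.0066) were identical. That is expected, because outcome and baseline covariate are both reflected and the fit is otherwise the same. Under B, the mean change was 2.20 and the contrast −1.56, with F 3.57 and p 0.014.

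**Link to missing items.** Filling a gap with the mean of the answered items is sensible only if all scored items run the same way. That is true of the intended key and of A, but not of B.

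**The case against.** The strongest reply is that the sentence need not be wrong. Reversal is relative, and the SAP does not say relative to what. The sentence may only flag the two items keyed opposite to the rest (D), or responses may be stored with the highest code for the least agreement (C). Both give the intended score. The preceding sentence fixes the direction, and an ambiguous note should be read consistently with it. A programmer who honoured both sentences would reject A. B adds a step the SAP does not state, since it singles out only two items. A fully inverted score would probably also look odd beside SF-36v2 Vitality, which Protocol 8.1.2.2 puts through the same ANCOVA.

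Much of this stands. A reader might infer that, followed as written, the fatigue endpoint points the wrong way. The documents do not support that: it needs upward agreement coding, and the other 11 items both fatigue-worded and summed as answered, and neither document says so. The stakes are also limited. The primary analysis is unaffected, no responder threshold is set for FACIT-F, full inversion leaves the ANCOVA p-value unchanged, and Protocol 5.6.1 describes the statistics as descriptive.

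Two parts do not stand. Relying on the direction sentence asks the programmer to resolve a conflict that the scoring rule itself creates, with no coding, item list or manual reference in 10.9 to resolve it. And an unchanged p-value is little comfort when the reported quantity is a signed mean change. Under B the direction looks right, so the error could easily pass unnoticed.

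**Conclusion.** The point holds in conditional form. On its literal reading, with upward agreement coding and the other 11 items fatigue-worded, the only item rule for FACIT-F contradicts the direction that the SAP and protocol state. The consequence is then either a complete sign change (52 minus the intended score) or, if all 13 items are reversed, a uniform gain that reads as 9 instead of 13. Under descending storage, or a relative meaning of reversal, the total is correct. Inversion is therefore a possibility left open by the text, not a demonstrated error.

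Severity is moderate. The rule feeds a secondary endpoint at Post-Treatment Weeks 12 and 24, and the exploratory label in SAP 10.9 does not change its listing in SAP 10.4. One sentence permits correct, attenuated or inverted results, and the stated range would not reveal which had been produced.

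**What to change.** Replace the sentence in SAP 10.9 with an explicit key that:

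- states how raw responses are coded;
- lists which items are computed as 4 minus response, so that 4 means least fatigue on every item.

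With upward agreement coding, the fatigue-worded items are reversed and items 7 and 8 are not. The coding has to be stated first, because the same instruction applied to descending codes would give N + (8 − P), which is the inverted score.

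Confirm the key against the scoring manual and cite it, as is done for SF-36v2. Before database lock, run two test records through the scoring program: the least-fatigued response pattern must score 52 and the most-fatigued 0. This check fails under both A (0 and 52) and B (44 and 8).

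The cost is a sentence or short table in the SAP and a two-record programming check. No data collection changes.

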11.0 Safety Analysis

11.1 General Considerations

All subjects who receive at least one dose of study drug in Study M14-222 will be included in the safety analyses.

11.2 Analysis of Adverse Events

11.2.1 Treatment-Emergent Adverse Events

Adverse events will be coded using the Medical Dictionary for Regulatory Activities (MedDRA). Treatment-emergent adverse events are defined as any event that begins or worsens in severity after initiation of study drug through 30 days after the last dose of study drug. Events where the onset date is the same as the study drug start date are assumed to be treatment-emergent. If an incomplete onset date was collected for an adverse event, the event will be assumed to be treatment-emergent, unless there is other evidence that confirms that the event was not treatment-emergent (e.g., the event end date was prior to the study drug start date).

11.2.1.1 Tabulations of Treatment-Emergent Adverse Events

Adverse event data will be summarized and presented using primary MedDRA system organ classes (SOCs) and preferred terms (PTs) according to the version of the MedDRA coding dictionary used for the study at the time of database lock. The actual version of the MedDRA coding dictionary used will be noted in the clinical study report. The system organ classes will be presented in alphabetical order and the preferred terms will be presented in alphabetical order within each system organ class.

Adverse Event Overview

An overview of adverse events will be presented consisting of the number and percentage of subjects experiencing at least one event for the following adverse event categories:

- Any treatment-emergent adverse event;

- Treatment-emergent adverse events with a "reasonable possibility" of being related to DAAs;
- Severe treatment-emergent adverse events;
- Serious treatment-emergent adverse events;
- Treatment-emergent adverse events leading to discontinuation of study drug;
- Treatment-emergent adverse events leading to interruption of study drug;
- Treatment-emergent adverse events leading to RBV dose modifications;
- Treatment-emergent adverse events leading to death;
- Deaths.

Adverse Event by SOC and PT

The following summaries of adverse events will be generated:

- Treatment-emergent adverse events;
- Treatment-emergent adverse events with a "reasonable possibility" of being related to DAAs;
- Serious treatment-emergent adverse events;
- Moderate or severe treatment-emergent adverse events;
- Severe treatment-emergent adverse events;
- Grade 3 or 4 (see definition below) treatment-emergent adverse events;
- Treatment-emergent adverse events leading to discontinuation of study drug;
- Treatment-emergent adverse events leading to interruption of study drug;
- Treatment-emergent adverse events leading to RBV dose modifications;
- Treatment-emergent adverse events leading to death;
- Treatment-emergent adverse events leading to concomitant medication use (events with other action taken of "concomitant medication prescribed").

For all adverse event summaries, the number and percentage of subjects experiencing treatment-emergent adverse events will be tabulated according to SOC and PT. Subjects reporting more than one adverse event for a given PT will be counted only once for that

term (most severe incident for the severity tables and most related incident for the relationship tables). Subjects reporting more than one adverse event within a SOC will be counted only once for that SOC. Subjects reporting more than one adverse event will be counted only once in the overall total.

A listing of treatment-emergent adverse events grouped by body system and preferred term with subject numbers will be created.

Adverse Event by PT

The number and percentage of subject experiencing treatment-emergent adverse events will be tabulated according to preferred term and sorted by overall frequency. Similar summaries will be provided for moderate to severe treatment-emergent adverse events and treatment-emergent adverse events with a "reasonable possibility" of being related to DAAs.

Adverse Event of Special Interest

Specific treatment-emergent adverse events of special interest, which may be searched using Standardized or Company MedDRA Queries, will be summarized. The search criteria for the adverse event of interest is as follows:

- Severe Cutaneous Reactions SMQ "Severe cutaneous adverse reactions" (narrow search)

The number and percentage of subjects experiencing at least one treatment-emergent adverse event in the search for the event of interest will be presented by SOC and PT.

A listing of treatment-emergent adverse events for subjects meeting the search criterion will be provided for the adverse event of special interest.

Adverse Event by Maximum Severity

Treatment-emergent adverse events and treatment-emergent adverse events with a "reasonable possibility" of being related to DAAs will be summarized by maximum

severity of each preferred term. If a subject has an adverse event with unknown severity, then the subject will be counted in the severity category of "unknown," even if the subject has another occurrence of the same event with a severity present. The only exception is if the subject has another occurrence of the same adverse event with the most extreme severity – "Severe." In this case, the subject will be counted under the "Severe" category.

Adverse Events by Maximum Severity Grade Level

Treatment-emergent adverse events will be summarized by maximum severity grade level of each preferred term. Each preferred term will be assigned to a grade level based on severity and seriousness, adapted from the Division of AIDS (DAIDS) table for grading severity of adverse events. All serious adverse events will be categorized as Grade 4. Nonserious adverse events categorized by the investigators as mild, moderate, or severe will be categorized as Grade 1, Grade 2, or Grade 3, respectively. If a subject has a nonserious adverse event with unknown severity, then the subject will be counted in the severity grade level category of "unknown," even if the subject has another occurrence of the same event with a severity present. The only exception is if the subject has another occurrence of the same adverse event with the most extreme severity – "Severe." In this case, the subject will be counted under the "Grade 3" category. Similarly, if a subject has an adverse event with unknown seriousness, then the subject will be counted in the severity grade level category of "unknown" unless the subject has another occurrence of the same adverse event that is marked serious. In this case, the subject will be counted under the "Grade 4" category.

Adverse Event by Maximum Relationship

Treatment-emergent adverse events also will be summarized by maximum relationship of each preferred term to study drug (DAA), as assessed by the investigator. If a subject has an adverse event with unknown relationship, then the subject will be counted in the relationship category of "unknown," even if the subject has another occurrence of the same event with a relationship present. The only exception is if the subject has another occurrence of the same adverse event with a relationship assessment of "Reasonable

Possibility." In this case, the subject will be counted under the "Reasonable Possibility" category.

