8.1.4.1 Adverse Events

Adverse events will be coded using the Medical Dictionary for Regulatory Activities (MedDRA). The number and percentage of subjects with treatment-emergent adverse events (i.e., any event that begins or worsens in severity after initiation of study drug through 30 days post-study drug dosing) will be tabulated by primary MedDRA System Organ Class (SOC) and preferred term (PT). The tabulation of the number of subjects with treatment-emergent adverse events by severity rating and relationship to study drug will also be provided. Subjects reporting more than one adverse event for a given MedDRA preferred term will be counted only once for that term using the most severe incident for the severity rating table and the most related for the relationship to study drug table. Subjects reporting more than one type of event within a SOC will be counted only once for that SOC.

Additional analyses will be performed if useful and appropriate.

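### In the maximum-grade adverse-event table, the missing-severity rule has no exception for a serious occurrence, so read literally it files a few certain Grade 4 subjects as unknown or Grade 3

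*SAP*

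**What the plan says.** The point lies in SAP 11.2.1.1, under Adverse Events by Maximum Severity Grade Level.

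- **What is tabulated:** "Treatment-emergent adverse events will be summarized by maximum severity grade level of each preferred term".
- **Grade 4:** "All serious adverse events will be categorized as Grade 4". The event's own severity rating plays no part.
- **Grades 1 to 3:** "Nonserious adverse events categorized by the investigators as mild, moderate, or severe will be categorized as Grade 1, Grade 2, or Grade 3, respectively".
- **Missing severity:** "If a subject has a nonserious adverse event with unknown severity, then the subject will be counted in the severity grade level category" of unknown, and this applies "even if the subject has another occurrence of the same event with a severity present".
- **Exception to that rule:** "The only exception is if the subject has another occurrence of the same adverse event with the most extreme severity", namely Severe. The subject is then counted as Grade 3.
- **Missing seriousness:** a parallel rule files the subject as unknown unless another occurrence is marked serious, in which case the subject is Grade 4.

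The general counting rule in the same section takes the most severe incident when a subject reports a preferred term more than once.

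**The concern.** On the grade scale the top category is Grade 4, and it is reached through seriousness. The missing-severity rule nevertheless makes its sole exception for Severe, which is the top of the three-level severity scale but only Grade 3 here. The override and the exception both refer to any other occurrence of the event; neither is limited to nonserious ones. A serious occurrence can therefore be overridden by a missing severity on a different, nonserious occurrence.

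The maximum is not in doubt for such a subject. A nonserious event cannot exceed Grade 3, whatever its missing severity was, so the serious occurrence fixes the maximum at Grade 4. The table would then undercount Grade 4 and could disagree with the serious-event table for the same subject and term. The SAP also plans a separate table of Grade 3 or 4 events that points to this definition. If that table uses the subject-level category, a subject filed as unknown drops out of it too; the SAP does not say which level it uses.

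The situation is possible because seriousness and severity are rated separately (Protocol 6.1.2 and 6.2). A hospitalisation makes a mild or moderate event serious.

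**Working it through.** The plan states no figure to reproduce here; the check is of a classification rule, followed by a rough size.

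**1. Enumerating the rule.** Give each occurrence one of 3 seriousness states (serious, nonserious, unknown) and one of 4 severity states (mild, moderate, severe, unknown), which makes 3 × 4 = 12 types. Two occurrences of one preferred term in one subject then form 12 × 13 / 2 = 78 unordered pairs. Pairs with no serious occurrence number 8 × 9 / 2 = 36, so 78 − 36 = 42 contain a serious one. Under the SAP's Grade 4 rule all 42 should be Grade 4.

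Applied literally, 38 of the 42 are Grade 4 and 4 are not:

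| Serious occurrence rated | Other occurrence | Filed as | Certain maximum |
|---|---|---|---|
| Mild | Nonserious, severity unknown | Unknown | Grade 4 |
| Moderate | Nonserious, severity unknown | Unknown | Grade 4 |
| Severity unknown | Nonserious, severity unknown | Unknown | Grade 4 |
| Severe | Nonserious, severity unknown | Grade 3 | Grade 4 |

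Two checks bound the defect. A serious event standing alone is Grade 4 even when its own severity is missing. A serious occurrence paired with one of unknown seriousness is Grade 4 in all 16 combinations, because that rule carries the exception.

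With a serious-occurrence exception added to the missing-severity rule, all 42 pairs become Grade 4. Exactly 4 of the 78 pairs change category and 74 do not.

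**2. Size.** Inputs: about 600 subjects, of whom 100 to 150 have F4 fibrosis (Protocol 5.1). Serious-event rates are from Protocol Table 2: 4.7% and 6.3% in the cirrhotic arms, and 1.4% to 2.2% in the active arms of the other studies.

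- Low: 100 × 4.7% + 500 × 1.4% = 4.7 + 7.0 = 11.7, about 12 subjects with a serious event.
- High: 150 × 6.3% + 450 × 2.2% = 9.45 + 9.9 = 19.35, about 19 subjects.

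The documents do not say how often a subject with a serious event also has a nonserious occurrence of the same term with missing severity. Assuming 1% to 5%:

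- Low: 11.7 × 1% = 0.12 subject.
- High: 19.35 × 5% = 0.97 subject.

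About 0 to 1 subject is misfiled.

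**The case against.** The best defence is one of order. The section settles Grade 4 first and without condition, then maps nonserious events to Grades 1 to 3, then deals with nonserious events of unknown severity. Read as a sequence, the missing-severity rule sorts out Grades 1 to 3 among nonserious occurrences, where Severe is the top. The table's aim of showing a maximum, and the most-severe-incident convention, point the same way.

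A sensible programmer may well do this, but the text sets no such order. It calls Severe the only exception, and where the authors wanted a serious occurrence to prevail, in the unknown-seriousness rule, they wrote it out. Two programmers could follow the SAP and produce different tables.

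Other parts of the defence stand. The trigger is narrow. Missing severity should be uncommon, since investigators must record severity for every event (Protocol 6.0) and data are cleaned before lock (SAP 4.4). Serious events keep their overview row, their own table and their listings (SAP 11.2.1.1 and 11.2.2). No efficacy endpoint depends on this table.

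Three stronger readings are tempting but unsupported:

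- A reader might infer that a serious event with missing severity loses its Grade 4. Alone, it does not; the trigger is a second, nonserious occurrence with missing severity.
- A reader might apply 6.3% to everyone, 600 × 6.3% = 38 subjects with a serious event. That is the rate for 12-week cirrhotic subjects, and F4 enrolment stops at 150.
- A reader might see a conflict with Protocol 8.1.4.1, which counts repeated terms "using the most severe incident for the severity rating table". That sentence governs the mild, moderate and severe table; the section plans no grade-level table.

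**Conclusion.** The missing-severity rule is wrong as written, in one narrow case: the same subject has, for the same preferred term, a nonserious occurrence of unknown severity and a serious occurrence. The literal result is unknown or Grade 3 where the maximum is certainly Grade 4, so Grade 4 can only be undercounted. The expected size is about 0 to 1 of 600 subjects. That rests on Phase 3 rates carrying over to this study and on an assumed 1-5% co-occurrence for which the documents give no basis. It does not follow that serious events go unreported or that any safety conclusion changes. Low priority.

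**What to change.** In SAP 11.2.1.1, add one exception to the missing-severity rule, placed ahead of the Severe exception and matching the one in the unknown-seriousness rule. For example: *A subject with any serious occurrence of the preferred term is counted as Grade 4, regardless of missing severity on other occurrences.* The words that make Severe the sole exception need adjusting to fit.

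The cost is one clause in the SAP and one condition in the table program. It changes only the four pair types shown above, and there is no evident downside. A full rewrite of the hierarchy is not needed for this defect.
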